#### **SCHEMA**

\* Patient may have started cycle #1 of Checkpoint Blockade up to 5 days prior and still be enrolled and randomized as long as SBRT occurs with Days 1-21 of Cycle #1 of checkpoint blockade.

# 1. PROTOCOL SYNOPSIS

TITLE	Randomized Phase II Study of Checkpoint Blockade Immunotherapy combined with Stereotactic Body Radiation Therapy in Advanced Metastatic Disease.
STUDY PHASE	Phase II
INDICATION	Patients who will receive CBI immunotherapy with at least 1 site of measurable metastatic disease which will not be irradiated.
PRIMARY OBJECTIVE	To determine whether SBRT combined with concurrent CBI improves the relative objective response rate (CR+PR) compared to CBI alone in patients with metastatic disease.
SECONDARY OBJECTIVES	
 
To assess the safety and toxicity of CBI used concurrently with SBRT delivered in 3 fractions in patients with metastatic disease
 
To determine the progression free survival, overall survival, and rate of stable disease greater than or equal to 6 months in patients after completion of SBRT in combination with CBI
 
To assess whether SBRT combined with concurrent CBI results in improvements in anti-tumor immune responses compared to CBI alone
 

HYPOTHESIS	Concurrent SBRT and CBI will increase the relative objective response (CR+PR) rate by at least 33% compared to CBI alone.
STUDY DESIGN	Patients who will receive CBI and have at least 1 site of measurable metastatic disease which will not be irradiated will be candidates for study. Patients will be randomized (1:1) to CBI combined with SBRT or CBI alone. SBRT at 9.5Gy x3 fractions will be delivered within 1-21 days of the start of Cycle #1 of CBI. The first six patients will be treated and observed for toxicity in the safety run-in phase for 30 days after radiation before continuing with further accrual. Radiation dose reduction is allowed if necessary to meet tissue constraints (6Gyx3 Minimum Dose). Response rates will be determined from the non-irradiated lesion/lesions and three blood draws will be obtained to analyze anti-tumor immune responses.
SAMPLE SIZE BY TREATMENT GROUP	73 patients per group (146 patients total)

SUMMARY OF SUBJECT ELIGIBILITY CRITERIA	
 
At least 1 site of measurable metastatic disease which will not be irradiated.
 
Plan to treat patient with CBI
 
Age ≥3 years.
 
Lansky scale score of ≥70 (ages ≥ 3 or < 16 years)         OR         Karnofsky scale score of ≥70 (ages ≥ 16 or < 18 years)         OR         ECOG performance status ≤ 2 (18 years or older).
 
Histologic confirmation of malignancy (primary or metastatic tumor).
 

CBI PRODUCT DOSAGE AND ADMINISTRATION	Commercially available checkpoint blockade immunotherapy will be administered intravenously as clinically indicated.
CONTROL GROUP	CBI Alone
PROCEDURES	1. Physical exam 2. Three Research Blood draws 3. CT or MRI of Involved Site 4. PET-CT (optional) 5. SBRT 6. IV CBI administration

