#### 6. TREATMENT PLAN

#### **6.1 Diagnostic Procedures**

A CT scan or MRI will be performed for tumor localization using rigid immobilization appropriate for stereotactic treatment. A separate PET-CT may be performed (optional) for diagnostic purposes and can be used for treatment planning with fusion – the identical study would be performed if the patient were having standard conventional dose radiation.

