#### 11.3 Disease Parameters

Measurable Disease: Measurable lesions are defined as those that can be accurately measured in at least one dimension (longest diameter to be recorded) as  $\geq 0.5$  cm with diagnostic techniques (CT, PET/CT (all are optional), or MRI). All tumor measurements must be recorded in centimeters.

Non-Measurable Disease: All other lesions (or sites of disease), including small lesions (longest diameter <0.5 cm with diagnostic techniques), are considered non-measurable disease. Bone lesions, leptomeningeal disease, ascites, pleural/pericardial effusions, lymphangitis, inflammatory breast disease, and cystic lesions are all non-measurable.

Target Lesions: Target lesion in this study will be considered metastatic sites up to a maximum of 3 lesions per patient. They should be recorded and measured at baseline. Target lesions should be equal to or larger than 1.0 cm in the smallest

cross-sectional diameter on CT or MRI and/or any lesion that shows increase metabolic uptake on PET/CT scans.

Non-Target Lesions: Non-Target lesion in this study will be considered metastatic sites up to a maximum of 10 lesions per patient. They should be recorded and measured at baseline. Non-target lesions should be equal to or larger than 0.5 cm in the smallest cross-sectional diameter on CT or MRI and/or any lesion that shows increase metabolic uptake on PET/CT scans. Importantly, a sum of the longest diameter (LD) for all *non-target* lesions will be calculated and reported as the baseline sum LD. The baseline sum LD of the *non-target* lesions will be used as reference by which to characterize the objective tumor response.

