#### 11.5 Response Criteria (via RECIST 1.1)

#### 11.5.1 Evaluation of Target Lesions

Complete Response (CR): Disappearance of all targeted and *Non-Targeted* lesions

Objective Response (OR): At least a 30% decrease in the sum of the

longest

diameter (LD) of targeted and *Non-targeted* lesions,

taking as reference the baseline sum LD

Progressive Disease (PD): At least a 20% increase in the sum of the LD of

Targeted or Non- Targeted lesions, taking as reference the smallest sum LD recorded since the treatment started or the appearance of one or more new lesions

Stable Disease (SD): Neither sufficient shrinkage to qualify for PR nor

sufficient

increase to qualify for PD, taking as reference the

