#### 12.3 Potential Adverse Events

Signs and symptoms of disease progression are not considered AEs. The development of a new cancer should be regarded as an AE. New cancers are those that are not the primary reason for administration of study treatment and have been

identified after inclusion of the patient into the clinical study.

Because patients are receiving standard treatments, which are not part of this study, their treating physician will be counseling them on the risk of their treatments, including the risk of surgery, radiation therapy, and/or chemotherapy, whichever is appropriate for the type and the stage of their cancer. The procedures related to the study are phlebotomy, PET imaging (all are optional), SBRT, and CBI administration.

Phlebotomy can cause pain, bleeding, and rare needle site infection. PET imaging results in low dose radiation exposure (see Investigator's Brochure for details of dosimetry), which has an extremely small risk of causing a secondary cancer.

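### Section 11.3 lets uptake on an optional PET-CT add a lesion to the scored set, and nothing keeps that scan equal between the arms

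*Combined protocol and SAP*

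**What the plan says.** - **PET-CT is optional.** The Procedures row of the synopsis reads "CT or MRI of Involved Site 4. PET-CT (optional"), with no arm named. Section 12.3 is similar: "The procedures related to the study are phlebotomy, PET imaging (all are optional), SBRT, and CBI administration".
- **Its stated purpose.** Section 6.1 says "A separate PET-CT may be performed (optional) for diagnostic purposes and can be used for treatment planning with fusion". The sentence follows the description of the localisation scan for stereotactic treatment.
- **Planning belongs to one arm.** Under 6.2, simulation and SBRT planning begin once a patient has been randomised to SBRT. The same section asks for RECIST measurements within 4 weeks before CBI starts.
- **How a lesion enters the lists.** Section 11.3 sets a minimum smallest diameter (1.0 cm for target, 0.5 cm for non-target lesions) and then, for both lists, adds an alternative: "cross-sectional diameter on CT or MRI and/or any lesion that shows increase metabolic uptake on PET/CT scans". The PET alternative has no size limit. The same section classes bone lesions and lesions under 0.5 cm as non-measurable.
- **What the lists feed.** In 11.3 the baseline sum of longest diameters of the non-target "lesions will be used as reference by which to characterize the objective tumor response", and 15.5 defines the primary endpoint on that sum. In 11.5.1 progression is a 20% rise over the "smallest sum LD recorded since the treatment started or the appearance of one or more new lesions".

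**The concern.** A randomised comparison of response needs the scored lesions to be found in the same way in both arms. Here a scan that some patients have and others do not can by itself add a lesion to the baseline sum. The clearest reason in the protocol for having that scan, radiation planning, arises only after allocation and only in the SBRT arm.

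Two outcomes are exposed. For response, an added lesion changes both the baseline sum and the later sum. For PFS, a lesion already listed at baseline cannot later count as new, whereas the same lesion in a patient without PET can, if a follow-up CT shows it.

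There is also a fault that does not depend on arm. Section 11.3 asks for diameters to be summed over a list that may contain lesions which the same section calls non-measurable.

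**Working it through.** **1. Does PET alone suffice?** Yes. In 11.3 the size rule and the PET rule are joined by and/or, so uptake without a qualifying CT/MRI diameter is enough.

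**2. When could a PET change the baseline set after allocation?** Section 6.2 normally places randomisation before CBI and baseline measurement within 4 weeks before CBI; 11.3 has lesions recorded at baseline. If these are followed, a PET done after CBI starts cannot add a baseline lesion. The open window runs from randomisation to the first CBI dose. It is closed for patients who began CBI up to 5 days before enrolment. Section 11.4 gives a different limit (6 weeks before treatment), and neither section requires the list to be fixed before randomisation.

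**3. Which lesions does the route add?** Non-target lesions of at least 0.5 cm in smallest diameter on CT or MRI qualify in both arms without PET. Inside the scanned field, PET therefore adds mainly lesions below 0.5 cm or otherwise non-measurable ones such as bone. Larger PET-only lesions arise only outside the field or when not recognised on CT. A lesion below 0.5 cm is also smaller than the 5 mm reconstruction that 11.4 specifies for spiral CT, so its diameter is poorly measured.

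**4. Can an added lesion change a response?** Illustrative sums, not trial data; response means a fall of at least 30%.

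| CT sum (mm) | Fall (mm) | Without PET lesion | PET-only lesion | With PET lesion |
|---|---|---|---|---|
| 40 | 14 | 14/40 = 35.0%, response | 4 mm, unchanged | 14/44 = 31.8%, response |
| 40 | 14 | 35.0%, response | just under 5 mm, unchanged | about 14/45 = 31.1%, response |
| 40 | 13 | 13/40 = 32.5%, response | 4 mm, unchanged | 13/44 = 29.5%, no response |
| 40 | 11 | 11/40 = 27.5%, no response | 4 mm, disappears | 15/44 = 34.1%, response |

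In the first case the unchanged addition would have to exceed 14/0.30 − 40 = 6.7 mm to remove the response. A single small lesion matters only near the cut-off, and it can act in either direction.

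**5. How sensitive is the primary test to a shift?** Inputs from the plan: 73 per arm; one-sided alpha, printed in 15.2 as 0.05% and read here as 0.05. As a check on that reading, the pooled-variance formula with continuity correction for 61% versus 81% at 80% power returns 146 in total, the plan's figure. (The tumour-type mix that 15.2 mentions cannot be reproduced, because its frequencies are not given.)

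Let δ be an assumed net artefact in the SBRT arm's response rate, with no true effect. Then type I error = Φ[(δ − 1.645·SE0)/SE1], where SE0 = √(2p̄(1−p̄)/73) and SE1 = √{[p0(1−p0) + p1(1−p1)]/73}, with p1 = p0 + δ and p̄ the mean of p0 and p1.

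For p0 = 0.40 and δ = 0.02: SE0 = 0.0814, SE1 = 0.0814, and Φ[(0.02 − 0.1339)/0.0814] = Φ(−1.40) = 0.081.

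| Assumed shift | Type I error, control rate 25% to 61% |
|---|---|
| +1 point | 0.064 to 0.066 |
| +2 points | 0.080 to 0.085 |
| +4 points | 0.123 to 0.135 |
| +6 points | 0.179 to 0.201 |
| −2 points | 0.027 to 0.030 |

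In the other direction, power for 61% with a 33% relative increase (61% × 1.33 = 81.1%) is 0.856 without a shift, 0.777 with −2 points and 0.575 with −6 points. These figures show what a shift would do. They do not show that one will occur.

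**The case against.** The strongest reply is that the protocol never makes PET an SBRT-arm procedure. Section 6.1 is headed as diagnostic and names diagnostic use first, and the synopsis and 12.3 list optional PET without naming an arm. Baseline measurements precede CBI, 11.4 keeps one technique per lesion over time, the imaging calendar is common to both arms, and a study radiologist reviews all responses. The 0.5 cm CT/MRI rule already catches most lesions that PET would show.

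Much of this stands, and it rules out four stronger readings that a reader might infer:

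- **That PET use does differ by arm.** This is an inference from SBRT-only planning; no section states it.
- **That PFS is biased towards SBRT.** A planning PET after baseline could instead reveal a new lesion in an SBRT patient, and a listed lesion that grows adds to the 20% rule. Section 6.3 schedules CT, not PET, at follow-up.
- **That a countable number of controls is affected.** Such a count multiplies three quantities absent from the documents: the PET gap between arms, the yield of extra lesions, and the share that become visible on CT. For example, 0.50 × 0.20 × 0.50 = 5%, about 4 of 73; other choices give 1 to 8. This says nothing specific about this trial.
- **That an unchanged 12 mm PET-only lesion turns a 35% fall into 14/52 = 27%.** Inside the CT field a roughly round 12 mm lesion already qualifies by size in both arms.

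What the reply does not answer is the rule itself. The same-technique requirement governs lesions already listed, not which lesions are found. The radiologist's review is not stated to be blinded to arm. Nothing equalises PET use or fixes the list before allocation.

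**Conclusion.** The concern holds in a limited form. Section 11.3 contains a stated rule under which an optional scan can alter the primary-endpoint sum, and the protocol leaves a window, from randomisation to the start of CBI, in which that scan is plausibly more common in the SBRT arm. The rule also conflicts with the section's own definition of non-measurable disease, whatever the balance between arms.

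The size and direction of any effect on response or PFS cannot be derived. Inside the scanned field the added lesions are mostly under 0.5 cm or otherwise non-measurable, so an effect on response from a single small lesion needs a patient near the 30% cut-off; a larger effect needs bone disease, lesions outside the field or lesions missed on CT. The conclusion rests on reading and/or as making either condition sufficient, and on the inference that planning prompts some PET scans. It should be corrected because the repair is cheap, not because a bias has been demonstrated.

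**What to change.** - **Section 11.3:** select target and non-target lesions in both arms only from the diagnostic CT/MRI taken before randomisation, lock that list before allocation, and delete the PET/CT alternative from both definitions.
- **Section 11.5.1:** a finding seen only on PET does not count as a new lesion until CT or MRI confirms it.
- PET-CT may still be used for SBRT planning.

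With the list fixed before allocation, any limit of the baseline CT/MRI falls on both arms alike.

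**Cost:** wording in two sections. Inclusion criterion 5.1.2 already requires measurable, non-irradiated disease on CT or MRI, so no scan is added, and the sample size is unchanged. The downside is that a few PET-only lesions are no longer scored.

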## 2. ABBREVIATIONS AND DEFINITIONS OF TERMS

Abbreviation	Definition
ADL	Activities of daily living
AE	Adverse event
BID	Twice daily
BSA	Body surface area
BMP	Basic Metabolic Panel
CBI	Checkpoint Blockade Immunotherapy
CBC	Complete blood count
CI	Confidence interval
CMAX	Maximum concentration of drug
CNS	Central nervous system
CRF	Case report/Record form
CR	Complete response
CTCAE	Common Terminology Criteria for Adverse Events
DLT	Dose Limiting Toxicity
DSMB	Data Safety Monitoring Board
ECG	Electrocardiogram
GI	Gastrointestinal

Hgb	Hemoglobin
HPF	High-power field
HTN	Hypertension
IRB	Institutional Review Board
IV	Intravenous
LLN	Lower limit of normal
LFT	Liver Function Tests
MTD	Maximum tolerated dose
OS	Overall survival
PLT	Platelet
PD	Progressive disease
PFS	Progression free survival
PR	Partial response
QD	Once daily
RECIST	Response evaluation criteria in solid tumors
RR	Response rate
SAE	Serious adverse event
SBRT	Stereotactic body radiation therapy
SD	Stable disease
TTP	Time to progression
ULN	Upper limit of normal
UNK	Unknown
WBC	White blood cell
WHO	World Health Organization

#### 3. OBJECTIVES

#### 3.1 Primary Objective

3.1.1 To determine whether SBRT combined with concurrent CBI improves the relative objective response rate compared to CBI alone in patients with metastatic disease.

#### 3.2 Secondary Objectives

- 3.2.1 To assess the safety and toxicity of CBI used concurrently with SBRT delivered in 3 fractions in patients with metastatic disease
- 3.2.2 To assess progression free survival, overall survival, and rates of stable disease greater than or equal to 6 months in patients after completion of SBRT in combination with CBI
- 3.2.3 To determine whether SBRT combined with concurrent CBI results in improvements in anti-tumor immune responses compared to CBI alone

#### 4. BACKGROUND

#### 4.1 Cancer Immunotherapy and Immune System

The primary modalities of cancer treatment are Surgery, Chemotherapy, and Radiation therapy. Unfortunately, cancer continues to rise as a primary cause of death in the United States because these current modalities are unable to cure most patients once cancer has metastasized[1]. Recently the field of immunotherapy has gained significant interest as basic science discoveries have been translated to FDA approved clinical therapies, including checkpoint blockade immunotherapy[2, 3]. Checkpoint Blockade Immunotherapy (CBI), including anti-CTLA-4 and anti-PD-1/PD-L1 antibodies, has received mainstream attention due to the potential for dramatic and durable clinical responses in certain patients with metastatic disease[4-6]. CBI is now FDA approved for melanoma and lung cancers and is helping to establish immunotherapy as a new fourth modality of cancer care. Unfortunately, not all patients respond to single agent or dual agent CBI and the activity of current agents appears to be limited to certain disease types. Thus the next logical step is combining CBI with surgery, chemotherapy or radiation therapy and understanding how to best incorporate immunotherapy into palliative and definitive treatment regimens[7, 8].

It is now widely accepted that the immune system plays a critical role in tumor biology, as described by the three E's of cancer immunoediting, elimination, equilibrium, and escape[9]. The term elimination represents the classical paradigm of immuno-surveillance, where the immune system is seeking and eradicating cells which have undergone malignant transformation. Equilibrium represents a dynamic state potentially lasting years where malignant cells under internal and external stress adapt and respond to survive while interacting and modulating the immune system. Tumor escape denotes a phase where select cancer cells have overcome barriers to continued growth and can proliferate and spread in an immunocompetent host. As these interactions between the immune system and cancer cells becomes better understood additional targets and strategies for immuno-modulation have been discovered and translated for clinical benefit. Immunotherapy aims to provide a highly specific, efficacious, and well tolerated anti-cancer therapy. However, until very recently most immunotherapy approaches have not proven to be very potent. Methods which enhance the induction and potency of the immune response are needed in order to continue the progress of immunotherapy in the clinic.

Development of an immune response is a complex and highly regulated process which involves interaction of multiple different cell types. In a simplified example, an antigen presenting cell (APC) such as a macrophage or dendritic cell (DC) captures an antigen which it then presents via MHC on the cell surface[10]. The APC then migrates back to a lymph node where it interacts with CD4 T-helper cells. The T-cell receptor binds to the antigen presented on MHC and in the presence of proper costimulation, a T- or B-cell is then signaled to propagate an immune response resulting in development of cytotoxic effector T-cells or tumor specific antibodies, respectively. There are classically two signals which are needed in order to induce a specific immune response: Signal 1 is the antigen; Signal 2 is the co-stimulatory

surface molecule. Professional APCs including DCs are the most potent antigen presenting cells capable of inducing immune responses due to their high antigen presentation capacity, high expression of co-stimulatory molecules and ability to secrete significant levels of co-stimulatory cytokines. The presence of these costimulatory molecules cannot be understated as DCs, which do not express costimulatory molecules, can cause T-cell anergy and actively suppress development of a specific immune response[10]. Unfortunately the tumor microenvironment is highly immunosuppressive and tumor cells use sophisticated mechanisms to inhibit immune responses. Indeed, there are a variety of different mechanisms used by tumors to suppress the immune response including physical barriers, loss of antigen or MHC, increasing expression of inhibitory cell surface molecules, secretion of inhibitory cytokines, and recruitment of suppressor cell populations such as T-regulatory cells (Tregs) or Myeloid derived suppressor cells (MDSC)[11-13]. The presence of these powerful inhibitory mechanisms highlights the need for combinatorial immunotherapy strategies to unlock the full potential of the immune system to fight cancer.

While immunotherapy is establishing itself as a novel and effective modality of cancer treatment, the current use FDA approved indication for CBI is in patients with metastatic disease. The ability for cancers to metastasize depends on a number of factors including histology, location, time, as well as the genetics or biology of the cancer. Interestingly, some aggressive tumors metastasize early in the course of disease while other cancers behave more indolently and may never metastasize. Along these lines there is a term called oligometastatic disease in which metastases are limited in number and location (for example only 3 lung metastasis, or only 2 liver metastasis). Although there is no strict definition of oligometastases, it is commonly interpreted to be no more than 5 or 6 metastatic sites. The presence of an oligometastatic state was originally coined by Hellman et al., who hypothesized that patients with olgiometastatic disease might derive benefit from effective local therapy applied to all sites of disease [14]. Clinical data has supported this hypothesis and the aggressive treatment of metastatic disease with surgery and chemotherapy in patients with isolated pulmonary metastases or liver metastases has resulted in long term survival[15-17]. The optimal type of treatment for metastases depends on a number of factors including histology, location, size, and number of sites. However, options for definitive local therapy include surgery (metastectomy), other ablative therapies such as radiofrequency ablation (RFA) or cryotherapy, specific targeted systemic therapies including hormonal therapy, or ablative radiation therapy (Stereotactic Body Radiation Therapy (SBRT). In this trial we are investigating combining checkpoint blockade immunotherapy with focused radiation therapy (SBRT) in attempt to enhance response rates and improve clinical outcomes for these patients.

